**A Pilot Study to assess
Spinal Cord Stimulation to Inhibit Afferent Feedback during Exercise in Hypertension**

Protocol Version: 11/27/2018

NCT02828436

Principal Investigator:

[name]., DPT, University of Minnesota

Study Summary

Title	A Pilot Study to Assess Spinal Cord Stimulation to Inhibit Afferent Feedback during Exercise in Adults with HTN
Short Title	SCS to Inhibit Afferent Feedback during Exercise
Protocol Number	1604M86961
Phase	Pilot Data
Methodology	Single blinded, randomized – order study
Study Duration	Two years
Study Center(s)	Single-center
Objectives	To investigate the exercise blood pressure response during a lower-extremity dynamic exercise in postmenopausal women with hypertension and to determine if lumbar epidural spinal cord stimulation reduces blood pressure during exercise in postmenopausal women and men with hypertension.
Number of Subjects	40
Diagnosis and Main Inclusion Criteria	Hypertension: Men and postmenopausal women between the ages of 40-90 years old. Hypertension as defined by BP \geq130/80 and diagnosed by a physician
Statistical Methodology	A two factor (condition x time) repeated measures ANOVA with sex as a between subjects factor.

List of Abbreviations

AE	adverse event
BP	blood pressure
CITI	Collaborative Institutional Training Initiative
CO	cardiac output
CT	computed tomography
CVD	cardiovascular disease
DSMB	data safety monitoring board
ECG	electrocardiogram
EPR	exercise pressor response
EXER	exercise
FSH	follicle-stimulating hormone
HIPAA	Health Insurance Portability and Accountability Act
HR	heart rate
HTN	hypertension
IRB	institutional review board
MAP	mean arterial pressure
MRI	magnetic resonance imaging
PI	principal investigator
RCO	regional circulatory occlusion
REC	recovery
RER	Respiratory Exchange Ratio
RPE	rating of perceived exertion
SAE	serious adverse event
SCS	spinal cord stimulation
SVR	Systemic Vascular Resistance
VE	ventilation
VO2	volume of oxygen uptake
VCO2	volume of carbon dioxide produced

Table of Contents

1. Introduction	5
1.1. Background and Significance.....	5
2. Specific Aims/Study Objectives.....	6
3. Investigational Device	7
4. Study Design	7
1.2. Study Design	7
1.3. Study Duration.....	8
2. Study Population	8
2.1. Inclusion Criteria.....	8
2.2. Exclusion Criteria.....	8
2.3. Recruitment	8
3. Study Visits	9
3.1. Pre-Screening	9
3.1.1. Screening and Baseline.....	10

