6.3. Adverse Event Reporting

The investigators will observe for adverse events at each session and conduct an interview at each session to determine whether an adverse event has occurred since the previous session. In addition, a follow-up phone call will be placed to each subject 2-3 days after the completion of the exercise and stimulation session to determine if any adverse events had occurred after the participant left the study.

6.3.1. **Serious Adverse Events (SAE) –**

A SAE is defined as any untoward medical occurrence, whether related to the study device or procedure or not, that meets one or more of the following criteria:

- Results in death
- Is life-threatening
 - Refers to an event in which the subject was at risk of death at the time of the event: it does not refer to an event that hypothetically might have caused death if it were more severe.
- Requires hospitalization > 24 hours
- Requires prolongation of existing hospitalization
- Results in persistent or significant disability/incapacity
- Results in fetal distress, fetal death, or congenital anomaly or birth defect

The relationship of the SAE to the study device and/or procedure will be evaluated by the investigator according to the following definitions:

- Unrelated: AE is not related to the study-specific devices or procedures
- Probably Related: AE has a strong temporal relationship to the study –specific devices or procedures, or another etiology is unlikely
- Unknown: Relationship of the study-specific devices or procedure and alternative etiology is unknown

Data for those SAEs determined to be “probably related” to the study devices or procedures, whether “expected” or “unexpected” will be collected and an emergent DSMB meeting will be held to determine if the study stopping rule criteria has been met. (section 7.4 and 7.5)

Otherwise all SAEs will be reported in summary form at the time of IRB continuing review.

6.3.2. *Unexpected Adverse Device Events (UADE)*

Any serious adverse effect on health or safety or any life-threatening problem or death caused by, or associated with, a device, if that effect, problem or death was not previously identified in nature, severity, or degree of incidence in the investigational plan or application (including a supplementary plan or application), or any other unanticipated serious problem associated with a device that relates to the rights, safety, or welfare of subjects.

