Problems/events that are unanticipated and involve new or increased risk to subjects should be reported to the IRB within 5 working days if, in the opinion of the PI, they are possibly, probably or definitely related to the research procedures.

Those serious, unanticipated problems/events that the PI deems unlikely or not related and do NOT meet the IRB’s definition of UPIRTSO and should be reported in summary form at the time of IRB continuing review.

6.3.3. *Expected Adverse Events (AE)*

Those adverse events identified as Potential Risks (section 9.2) will be collected and reported in summary form at the time of IRB continuing review Data and Safety Monitoring Board (DSMB)

The DSMB will consist of one physician, one faculty member familiar with spinal stimulation and one biostatistician. None of the Board members will be directly involved with the study. The DSMB will meet semiannually to review all reportable events. If a SAE related to the study devices or procedures occur, an emergent DSMB meeting will be held to assess whether the event meets the stopping rule criteria.

6.3.4. *Stopping Rules*

If a SAE occurs, that is deemed by the PI as being **related to the study devices or study procedure**; the study will be put on hold and reviewed by the DSMB to determine whether the study can continue.

6.4. *Protocol Deviations/Violations*

Any deviation from the investigational plan to protect the life or physical well-being of a subject in an emergency shall be reported to the IRB within 5 working days after the emergency occurred. Otherwise, deviations not meeting UPIRTSO criteria should be reported in summary form at the time of IRB continuing review.

7. Bibliography

2. **Borg GA.** Perceived exertion. *Exerc Sport Sci Rev* 2: 131-153, 1974.

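### Only the investigator's relatedness call brings an SAE promptly to the DSMB or pauses the study; SAEs graded unrelated or unknown have no prompt route to the board

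*Combined protocol and SAP*

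**What the plan says.** Section 6.3.1 gives attribution to one party: "The relationship of the SAE to the study device and/or procedure will be evaluated by the investigator". There are three grades: unrelated, probably related and unknown. The last is defined as "Unknown: Relationship of the study-specific devices or procedure and alternative etiology is unknown".

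For SAEs graded probably related, "an emergent DSMB meeting will be held to determine if the study stopping rule criteria has been met", with a pointer to sections 7.4 and 7.5. For the rest, "Otherwise all SAEs will be reported in summary form at the time of IRB continuing review".

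The DSMB paragraph in 6.3.3 describes a board of one physician, one faculty member who knows spinal stimulation and one biostatistician, none directly involved in the study. It meets twice a year on reportable events, a term the protocol does not define. If a related SAE occurs, "an emergent DSMB meeting will be held to assess whether the event meets the stopping rule criteria". This paragraph does not say who decides relatedness.

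The stopping rule in 6.3.4 is one sentence. It opens "If a SAE occurs, that is deemed by the PI as being" related to the device or procedure, and provides that the study is then paused while the DSMB decides whether it may go on.

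**The concern.** The board is independent and has the relevant expertise, but every prompt route to it passes through the investigator's own judgement. An SAE graded unrelated or unknown neither pauses the study nor calls a meeting, whatever its nature, and nothing in the text lets the board question the grade at the time.

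This matters in this population. Section 1.1 says that hypertensive adults face a raised risk of cardiovascular and cerebrovascular events during exercise or just after it. Underlying disease is therefore a ready explanation for some of the events the study procedures might cause. Participants are aged 40 to 90 and receive epidural leads, an arterial line and cuffed exercise. Section 1.1 describes the study as the first of its kind in hypertension, and its supporting figure covers 3 women and 5 men, all young and healthy. In a study this small, one misattributed SAE could be a large part of the safety information. If the attribution is wrong, sessions continue without an independent look.

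**Working it through.** The point rests on the text, and the plan states no figure to reproduce. Following each grade through 6.3.1, 6.3.3 and 6.3.4 gives:

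| Investigator's grade | Emergent DSMB meeting | Study hold | Other written route |
|---|---|---|---|
| Probably related | Yes (6.3.1, 6.3.3) | Yes, once the PI deems it related (6.3.4) | – |
| Unknown | No | No | IRB continuing-review summary; possibly the semiannual DSMB meeting |
| Unrelated | No | No | Same as for unknown |

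**Is there any trigger that does not depend on attribution?** None is written. No event type (such as death or paralysis), count, rate or threshold appears in 6.3. The five-working-day IRB report in 6.3.2 also depends on the PI's opinion, and it goes to the IRB, not to the DSMB.

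**What are the stopping criteria?** Sections 6.3.1 and 6.3.3 ask the board whether they are met. The pointer to 7.4 and 7.5 leads nowhere, because section 7 is the bibliography. It may be a numbering slip for the 6.4 and 6.5 in the table of contents, which are the stopping rules and protocol deviations. Even read that way, the only stopping-rule text is 6.3.4, and its only condition is the PI's relatedness call, which has already convened the meeting.

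**Are the relatedness terms consistent?** No. Section 6.3.1 uses probably related, 6.3.3 and 6.3.4 use related, and 6.3.2 uses a scale of possibly, probably and definitely. The SAE scale has no grade of possibly, and the protocol does not say where unknown falls on the 6.3.2 scale.

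**Scale of the delay.** Inputs are up to 60 subjects (section 1.2), about 2.5 years or 30 months of enrolment (section 1.3), 40 subjects per arm (20 women and 20 men, section 3.1.1) and DSMB meetings every 6 months (6.3.3). Enrolment is assumed to be even.

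- Enrolees between meetings: 60 / 30 × 6 = 12.
- Stimulation sessions between meetings, if 40 receive SCS: 40 / 30 × 6 = 8.
- With the Study Summary's 40 subjects over two years instead: 40 / 24 × 6 = 10 enrolees.

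An SAE graded unrelated or unknown just after a meeting could therefore wait up to six months, during which about 10 to 12 subjects enrol. This supposes that it counts as reportable at the next meeting. If it does not, the wait depends on the IRB's continuing-review interval, which the protocol does not state.

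**The case against.** The strongest reply is the definition of probably related. It is met by a strong temporal relationship, or by another cause being unlikely, so timing alone suffices. A cardiovascular event during a session or directly after it should qualify even where underlying disease is a competing explanation, and it should then reach the board at once. This stands and narrows the concern. It does not remove it, because the investigator applies the definition unchecked, and delayed events and those graded unknown stay outside the trigger.

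A reader might infer that the stopping rule is wholly circular and that the board merely repeats the PI's call. The text does not support that. The last clause of 6.3.4 gives the board an open decision on whether the study continues. The defect is narrower: the criteria named in 6.3.1 and 6.3.3 have no content of their own.

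A reader might also infer that the board never sees an SAE called unrelated. That is not established either. Reportable events is undefined, all SAEs are reported in some form, and the semiannual meeting may cover them. What is missing is prompt review.

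The five-working-day IRB report sets a lower bar, since possibly related is enough. It is a genuine second safeguard, but it covers only unanticipated events with new or increased risk and rests on the same person's opinion.

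Finally, it is tempting to turn the delay into a probability of further harm. The protocol gives no SAE rate and no chance of misattribution, so such a figure would rest on assumption alone.

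**Conclusion.** The concern holds in a limited form. Prompt DSMB review and the study hold occur only when the investigator or PI grades an SAE as related or probably related. SAEs graded unrelated or unknown have no prompt route to the board, and the stopping criteria the board is asked to apply say nothing beyond that grade.

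The practical gap is mainly delayed events, events graded unknown, and any in-session event where the timing test is misapplied. Its scale is about 12 enrolees, or about 8 stimulation sessions if 40 receive SCS, per six months under even enrolment. These figures describe exposure during a possible delay, not expected harm.

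The documents do not require the board's attribution to replace the investigator's; that would be a governance preference. Letting the board see every SAE and disagree is enough to close the gap, and it is worth doing because the board already exists.

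**What to change.** - In 6.3.1, send every SAE from the first study procedure to the last safety contact promptly to the existing DSMB, with the investigator's attribution, whatever the grade. State that the board may disagree with the attribution and call for the same hold and review. Keep the immediate hold when the PI calls an SAE related.
- To give that window a clear end, reconcile the follow-up call, which is 2–3 days after the session in 6.3 but 3–6 days in the schedule of assessments.
- In 6.3.3, define reportable events for the semiannual meetings to include all SAEs.
- In 6.3.1 and 6.3.3, replace the reference to stopping rule criteria with the decision 6.3.4 already gives the board, namely whether the study can continue. Correct the pointer to 7.4 and 7.5.
- Use one set of relatedness terms across 6.3.1 to 6.3.4, and say how unknown is handled.

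The cost is protocol wording and an occasional email or telephone review. The downside is that a few plainly unrelated SAEs will also need a short remote look by the board.
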